7.8 Long-term follow-up assessments

Trial closure data collection: After the 31st day after the final recruited participant has undergone their transplant the trial manager will telephone each of the PI to confirm the survival status of each recruited patient and, where a patient has died, the time to death will be measured from the date of their transplant and will be reported for all deaths due to all causes. The cause of death is to be recorded in all instances. The trial manager will also confirm with each PI the total length of in-hospital stay of any patient whose initial ICU or in-hospital stay was longer than 30 days. This should be completed within 4 weeks of the Trial Closure date.

There will be no additional long-term follow-up assessments related to participation in this trial. Long-term follow-up post-transplant is routine and life-long but will not be altered in any way as a result of participation in this trial.

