3.3.2 Secondary endpoints

- i. The proportion of eligible recipients who consent to take part in the study.
- ii. The proportion of eligible donor cardiac allografts where randomisation occurs according to the Protocol.
- iii. The proportion of eligible donor cardiac allografts where the heart is preserved in the correct randomly allocated solution.
- iv. Key outcome completeness
- v. The development of Primary Graft Dysfunction, according to the 2014 ISHLT Consensus Definition(2), within 24 hours of transplant implantation.
- vi. Echocardiographic parameters from trans-oesophageal echo immediately after transplant implantation, including:
 - a. Left Ventricular ejection fraction
 - b. Left ventricular maximal posterior wall thickness
 - c. Maximal septal wall thickness
 - d. Left ventricular function
 - e. Right ventricular function
 - f. The presence/absence of regional wall motion abnormalities
- vii. 30-day all-cause mortality.
- viii. 6-month survival rates, determined at the end of the study.
- ix. Development of the following post-operative complications will be recorded:
 - a. Dysrhythmias (defined by the clinical team) within 30-days of transplant implantation
 - b. Myocardial Infarction (defined according to ESC definitions of myocardial infarction post cardiac surgery) within 30-days of transplant implantation
 - c. Stroke (defined by radiological evidence of ischaemia/haemorrhage and clinical symptoms of stroke) within 30-days of transplant implantation
 - d. Transplant rejection (defined by the clinical team and confirmed on histopathology of biopsy material or post-mortem) within 30-days of transplant implantation
 - e. The need for post-operative renal replacement therapy within 30-days of transplant implantation
 - f. Infection (from any source requiring antibiotic therapy) within 30-days of transplant implantation
 - g. Venous thromboembolism (defined by radiological evidence and need for treatment) within 30-days of transplant implantation
 - h. Re-admission to any UK hospital within 30 days of transplant implantation
 - i. Hyponatraemia within 24 hours of transplant implantation (Na<125mEq/L on any serum laboratory-analysed sample, not blood gas analysis)
- x. Median length of initial ICU stay in hours
- xi. Median length of initial hospital stay in days

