*Where multiple Swan Ganz measurements are taken within the first 24 hours after transplant, the set of variables taken at the same time as the highest inotrope score should be uploaded to the CRF. Where there are multiple Swan Ganz measurements with the same inotrope score the set of variables with the lowest cardiac output should be uploaded to the CRF.

The following echocardiographic parameters from trans-oesophageal echo immediately after transplant implantation will be recorded in the initial outcome data collection CRF:

- i. Left Ventricular ejection fraction (% estimated by Simpson's biplane method)
- ii. Left ventricular maximal posterior wall thickness (in mm)
- iii. Maximal septal wall thickness (in mm)
- iv. Left ventricular function (good, moderate, poor or very poor)
- v. Right ventricular function (good, moderate, poor or very poor)
- vi. The presence/absence of any regional wall motion abnormalities as determined by the TOE operator

30-day outcome data collection: The delegated individual(s) in the recipient centre should upload the 30-day mortality, postoperative complication, length of initial ICU stay, and length of initial hospital stay data, on the 31st day after the transplant procedure. This should be conducted in accordance with the blinding instructions laid out in section 7.4 of this Protocol. The variables will be entered into the CRF as follows:

- i. 30-day mortality: alive/dead
- ii. Post-operative complications:
 - (i) Dysrhythmias (any within 30 days):
 - 1. Atrial fibrillation yes/no
 - 2. Ventricular tachycardia yes/no
 - 3. Ventricular fibrillation yes/no
 - 4. Other rhythm abnormality yes/no (specify)
 - (ii) Myocardial Infarction within 30 days (defined according to ESC definitions of myocardial infarction post-cardiac surgery): yes/no

- (iii)Stroke within 30 days (defined by radiological evidence of ischaemia/haemorrhage and clinical symptoms of stroke): yes/no
- (iv)Transplant rejection within 30 days (defined by the clinical team and confirmed on histopathology of biopsy material or post-mortem): yes/no
- (v) Infection within 30 days (from any source requiring antibiotic therapy): yes/no (specify suspected source)
- (vi) Venous thromboembolism within 30 days (defined by radiological evidence and need for treatment): yes/no (specify PE/DVT)
- (vii) 30-day re-admission to any UK hospital: yes/no
- (viii)Hyponatraemia within 24 hours of transplant (Na<125mEq/L on serum sample, not blood gas analysis): yes/no

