- (ix) Need for renal replacement therapy (continuous veno-venous haemofiltration or dialysis): yes/no
- iii. Length of initial[†] ICU stay in hours
- iv. Length of initial[†] in-hospital stay in days with admission to ICU taken as the first day and the day of discharge home as the final day, counting inclusive of both.

[†]Initial refers to the first stay only. For example, if a patient is discharged from ICU after 24 hours but re-admitted after 48 hours, the outcome assessor would only record 24 hours as the length of initial ICU stay. Similarly, where a patient is discharged from hospital after 5 days, this would be recorded as 5 days, even if they are subsequently re-admitted and have a longer overall length of stay.

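### The closure call asks for total hospital stay, so it does not complete an initial ICU stay still open at day 31 and does not match the first-stay definition (minor)

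*Protocol*

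**What the plan says.** Protocol 3.3.2 lists two length-of-stay endpoints: x, "Median length of initial ICU stay in hours", and xi, "Median length of initial hospital stay in days".

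Protocol 7.7 has sites upload "length of initial ICU stay, and length of initial hospital stay data, on the 31st day after the transplant procedure". Its footnote fixes the meaning: "Initial refers to the first stay only". A patient discharged and later re-admitted keeps the first figure "even if they are subsequently re-admitted and have a longer overall length of stay". The protocol therefore separates initial stay from overall stay.

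Protocol 7.8 describes a closure call after the last participant's 31st day. The trial manager is to "confirm the survival status of each recruited patient", with time and cause of any death, and also to "confirm with each PI the total length of in-hospital stay of any patient whose initial ICU or in-hospital stay was longer than 30 days". The section then states: "There will be no additional long-term follow-up assessments related to participation in this trial".

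Two other places bear on the point. The endpoint table in 3.3.4 appears to place endpoints x and xi at the end of recruitment. Section 10.8 sends a telephone query to the site when data are missing at CRF submission. A value that cannot be completed is taken as missing at random and is not imputed.

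**The concern.** The call in 7.8 exists because some stays will still be open at the day-31 entry. Its trigger names both ICU and hospital stay, but the only duration it asks for is a hospital one. If 7.8 is followed as written, endpoint x has no scheduled completion for a patient still in ICU at day 31. An analysis plan cannot recover a duration that nobody was asked to record.

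The second mismatch is one of definition. Endpoint xi is the first stay only, whereas 7.8 asks for the total.

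An ICU value lost in this way is missing because it is long, so the missing-at-random assumption in 10.8 does not suit it. The protocol's own figures (section 2: ICU medians of 14 days with PGD and 5 without) suggest that most such patients would have PGD. Section 4 says that the design replicates the larger trial except for its primary outcome, so the gap could carry forward.

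**Working it through.** **1. Items side by side**

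| | ICU stay | Hospital stay |
|---|---|---|
| Endpoint (3.3.2) | initial, hours | initial, days |
| Day-31 entry (7.7) | initial | initial |
| Trigger for the closure call (7.8) | initial, over 30 days | initial, over 30 days |
| Item collected on the call (7.8) | none | total |

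A stay that ends by the day-31 entry is captured. The gap concerns stays still open at that entry.

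**2. How many patients**

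The protocol states no figure for this, so there is none to reproduce. Inputs from the protocol: ICU medians of 14 days (PGD) and 5 days (no PGD), section 2; PGD 36%, sections 7.10 and 10.2; 50 patients, section 10.1. Assumption: log-normal stays with log-SD s from 0.6 to 1.0.

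Formula: P(stay > 30) = 1 − Φ(ln(30/median)/s).

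For s = 0.6:
- PGD: ln(30/14)/0.6 = 1.270, giving 0.102.
- No PGD: ln(30/5)/0.6 = 2.986, giving 0.0014.
- Weighted: 0.36 × 0.102 + 0.64 × 0.0014 = 0.038, and 50 × 0.038 = 1.9 patients.

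| s | PGD | No PGD | Overall | Of 50 | Share with PGD | P(at least one of 50) |
|---|---|---|---|---|---|---|
| 0.6 | 0.102 | 0.001 | 0.038 | 1.9 | 98% | 0.85 |
| 0.8 | 0.170 | 0.013 | 0.069 | 3.5 | 88% | 0.97 |
| 1.0 | 0.223 | 0.037 | 0.104 | 5.2 | 77% | 0.996 |

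An exponential shape with the same medians, P = 2^(−30/median), gives 0.226 and 0.016, or 9.2% overall and 4.6 of 50. The counts are for stays over 30 days; those still open at the day-31 entry would be slightly fewer. The protocol gives no distribution for hospital stay, so no count is offered for endpoint xi.

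**3. Effect on the reported medians**

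Compare an arm with 36% PGD against one with 22% (the section 2 planning rates), using the mixture of the two log-normals.

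| s | Median difference, all stays | Stays over 30 days dropped | Change |
|---|---|---|---|
| 0.6 | 1.00 day | 0.86 day | 0.14 |
| 1.0 | 0.99 day | 0.63 day | 0.36 |

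If open stays are instead ranked as longer than 30 days, an arm of 25 keeps its median unless at least 13 patients exceed 30 days. The binomial probability of that is 1.6 × 10⁻⁷ at a 10% rate, 0.0004 at 20% and 0.017 at 30%.

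**4. Effect on means**

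Section 10.3.3 plans Welch t-tests for continuous outcomes, so means matter too. Dropping stays over 30 days reduces the mean difference from 1.51 to 1.07 days (s = 0.6) or from 2.08 to 0.68 days (s = 1.0).

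**The case against.** The strongest reply is that this is loose drafting. The 7.8 trigger names ICU stay, so the call was evidently meant to complete open stays of both kinds. The CRFs are not shown and may have an ICU field. The endpoint table appears to set x and xi at the end of recruitment, not at day 30. Section 10.8 adds a site query, so 7.8 is not the only later contact. For someone whose first stay passed day 30, *total* may simply mean the full length of that stay. How open stays are analysed can be left to the SAP.

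Much of this stands, and it rules out three stronger readings that a reader might infer:

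- *That long ICU stays can never be measured.* The documents show only that no scheduled item asks for them. The table suggests an intention to complete them, but names no means of doing so. A query at CRF submission cannot complete a stay still running that day.
- *That hospital stays of long-stay patients are necessarily on another definition.* The readings diverge only for a patient re-admitted after a first stay over 30 days. The wording does not settle which is meant.
- *That the arm with more PGD would look materially better.* The endpoints are medians. Even with deletion, a shift of 0.1 to 0.4 day compares with a sampling SD of about 1.9 to 2.8 days for the median difference at 25 per arm. For means, a shift of 0.4 to 1.4 days compares with a standard error of about 2.4 to 5.6 days.

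What does not fall away is that the stated collection rule does not deliver the stated endpoint.

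**Conclusion.** The point holds as a minor correction to two secondary endpoints. As written, 7.8 leaves endpoint x without a scheduled value for anyone still in ICU at the day-31 entry, and its *total* conflicts with the first-stay rule behind endpoint xi. The situation is likely to arise: about 2 to 5 of 50 patients, with at least an 85% chance of one or more. This rests on the log-normal assumption with log-SD 0.6 to 1.0 and on the protocol's own medians and PGD rate. The effect on the reported medians is small if such patients are dropped and practically nil if they are ranked as longer than 30 days; means and t-tests are more exposed. The primary feasibility outcome and its success thresholds do not use length of stay and are unaffected.

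**What to change.** In Protocol 7.8, for every patient whose stay was still open at the day-31 entry, have the closure call collect:

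- the length of the initial ICU stay in hours, and
- the length of the initial in-hospital stay in days,

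both under the 7.7 footnote. Replace *total* with *initial*. State that a stay still open at the call is recorded as its duration to that date and flagged as ongoing, not entered as missing. The method of analysing flagged stays can remain with the SAP.

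The cost is a wording change in one section and, if they are not already there, two closure-CRF fields and an ongoing flag. The call is already planned, so no visit or patient burden is added.

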7.9 Qualitative assessments

As this is a feasibility trial, our primary outcome will be determined by numeric proportions and supplemented by qualitative assessments as follows:

Recipient decline to consent: Where an eligible recipient declines to consent to participate, the delegated individual(s) taking informed consent should document the reason for decline to consent, where provided (free text). The potential participant must be informed that they do not need to provide a reason.

Randomisation failure: Where an eligible recipient has provided consent to participate in this study and receives an eligible transplant that has not been randomised, the reason for failure to randomise should be recorded by the delegated individual(s) in the recipient centre.

Treatment allocation failure: Where an eligible recipient has provided consent to participate in this study and receives an eligible transplant that has been randomised but the incorrect treatment has been applied, the reason for the application of the incorrect treatment should be recorded by the delegated individual(s) in the recipient centre.

Blinding: Delegated individual(s) who record data in the CRFs will be asked whether they could have been blinded to the treatment allocation. Data from these questions will be assessed to determine the feasibility of blinding outcome assessors in the larger trial.

7.10 Withdrawal criteria

Responsible clinician withdrawal: The clinician responsible for a patient may withdraw the patient from the trial at any time for appropriate medical reasons. As the treatment provided as part of this trial is a one-off dose provided before the transplant is conducted, there is unlikely to be any event in which this is the case. Should a clinician responsible wish to withdraw their patient from the trial for appropriate medical reasons they should inform their local PI, documenting their reasons in the medical notes and complete the withdrawal CRF, indicating whether it is a complete or partial withdrawal.

MHRA status: Should either treatment be subject to a change in MHRA regulatory status during the recruitment period the trial will be halted. The change in regulatory status will be discussed with the sponsor and DMC. The trial will only be re-commenced upon agreement of the sponsor, DSMC and MHRA. All participants who had received the treatment prior to the halting of the trial would continue to receive normal post-transplant care and would not be withdrawn from the study.

DSMC concern: Where the DSMC has concerns about one of the treatments, the trial will be halted. A concern would be raised with a primary graft dysfunction rate >50% (based on the current UK estimated PGD rate of 36%) or a 30-day survival rate <88.8% (based on the 95% confidence interval for the median 30-day survival rate after cardiac transplant in the UK currently – NHSBT figures 2020-2021).

As this trial is concerned with the feasibility of recruiting and maintaining participants within the Protocol, any withdrawal from the trial should result in the local PI and CI being informed and the reason for withdrawal should be fully documented in the medical notes.

Where a post-transplant participant is withdrawn within the recruitment period, this participant will not be replaced and, for the purposes of the primary outcome, would be considered as having had a successful primary outcome where the criteria for this had been met.

Early cessation would be considered if there was a 30% absolute risk reduction in primary graft dysfunction in one treatment arm, as this is the point at which there would be sufficient power to confidently confirm that one arm reduced primary graft dysfunction with a 5% significance level at 80% power. Early cessation will also be considered where the DSMC has concerns that one treatment leads to a significant increase in SARs and/or SAEs.

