4 TRIAL DESIGN

This is a feasibility study of a single-blind, national, multi-centre, randomised controlled trial. The purpose of the trial is to assess the methodology and feasibility of conducting an appropriately powered efficacy randomised controlled trial comparing Custodiol-HTK with St Thomas' solution for donor cardiac allograft preservation during cardiac transplantation. The design, therefore, replicates a larger efficacy randomised controlled trial, differing only in its primary outcome, as described above.

The trial will be conducted at all six UK adult cardiothoracic transplant centres. Donor hearts included in the study will be randomly allocated on a 1:1 basis to receive either Custodiol-HTK or St Thomas' solution as cardioplegia and preservative solution during the organ retrieval process. Participants (recipients of donor cardiac allografts that have received one of the above treatments as part of the random allocation process) will be blinded to their treatment allocation. It is not possible to blind the healthcare staff involved in the transplant process as the solutions have different volumes and methods of administration and are different colours. Healthcare staff who look after the recipient but were not directly involved in the transplant retrieval or implant procedures should not be informed of the treatment allocation.

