10 STATISTICS AND DATA ANALYSIS

10.1 Sample size calculation

This is a feasibility study, so formal sample size calculation is not required. However, 50 hearts will give a 95% confidence interval of 53%-79% assuming a primary outcome rate of 66%.

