10.6 Interim analysis and criteria for the premature termination of the trial

Interim analysis will not routinely be performed. If interim analysis is requested by the Data Safety and Monitoring Committee then this will be performed by the DSMC's independent statistician.

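### The halting and early-cessation triggers in section 7.10 act on raw observed rates that chance can readily cross in arms of 25 or fewer

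*Protocol*

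**What the plan says.** Protocol section 7.10 contains two kinds of trigger.

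- **Efficacy.** "Early cessation would be considered if there was a 30% absolute risk reduction in primary graft dysfunction in one treatment arm". The reason given is that at this point one arm's benefit could be confirmed "with a 5% significance level at 80% power". The sentence gives no base rate, number of patients, test or sidedness.
- **Safety.** "Where the DSMC has concerns about one of the treatments, the trial will be halted". Then: "A concern would be raised with a primary graft dysfunction rate >50" per cent, or with 30-day survival below 88.8%. The PGD limit is "based on the current UK estimated PGD rate of 36" per cent. The survival limit is taken from a 95% confidence interval for the national figure. No minimum number of patients or interval is attached, and the text does not say whether the rates are per arm.

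Section 10.6 says "Interim analysis will not routinely be performed", but allows one at the DSMC's request, done by its independent statistician. It does not refer to 7.10.

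**The concern.** Power is a property of a test at a fixed sample size when a given true difference exists. Section 7.10 uses it to justify acting on an observed difference, at a time that is by definition before full enrolment.

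The safety limits have a related problem. A raw rate in 10 to 25 patients varies widely by chance, and a limit taken from the confidence interval of a national rate does not allow for that. Because the consequence is written as a halt, the trial could be stopped while both solutions perform exactly at the national rate. Recruitment would be interrupted, and the feasibility estimate the trial exists to produce would rest on fewer hearts.

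**Working it through.** **Inputs**
- Base PGD rate 36% (7.10). A 30-point reduction gives 6%.
- 50 hearts (10.1: "50 hearts will give a 95% confidence interval of 53%-79% assuming a primary outcome rate of 66" per cent), "randomly allocated on a 1:1 basis to receive either Custodiol-HTK or St Thomas' solution" (section 4), hence 25 per arm. This takes all 50 as randomised and assessed.
- 5% significance. Two-sided is assumed, as for the main-trial power in 10.2.
- Tests for PGD: Fisher exact or score (10.3.3).
- True 30-day survival is not in the documents. Assumed 93%, range 91% to 95%.

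**1. Reproducing the 80%**

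SE = √[(0.36×0.64 + 0.06×0.94)/25] = √(0.2868/25) = 0.1071.

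Power = Φ(0.30/0.1071 − 1.960) = Φ(0.841) = 0.800.

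The arcsine formula also gives 0.800, and the score test by exact enumeration gives 0.805. The stated figure therefore reproduces. It depends on the method: pooled variance gives 0.756 and Fisher gives 0.678.

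**2. What the 80% does not cover**

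At 10 per arm, power for the same true effect is 0.37 (pooled) to 0.43 (unpooled). At 25 per arm, an observed gap of at least 30 points needs 8 patients (8/25 = 32%). If 36% versus 6% is true, that happens in only 50% of trials, so the trigger is not a point of 80% power.

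Chance of an observed gap of at least 30 points, in either direction, with both arms truly at 36% (exact binomial):

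| Patients per arm | Probability |
|---|---|
| 10 | 24% |
| 20 | 7% |
| 25 | 2.6% |
| Checked after every pair from 10 per arm (simulation) | 30% |

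Example: 4/10 versus 1/10 meets the rule with Fisher p = 0.30.

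**3. PGD above 50%, both arms truly at 36%**

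At 25 per arm the limit is crossed by 13 or more cases: P(X ≥ 13) = 0.0745 for X ~ Bin(25, 0.36). For at least one of two arms, 1 − (1 − 0.0745)² = 14%.

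At 10 per arm (6 or more cases): 0.107 for one arm, 20% for at least one. Checked after every patient from the 10th per arm: 42% (simulation).

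Pooled over 50 patients (26 or more cases): 1.5%.

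**4. 30-day survival below 88.8%**

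Three deaths in 25 give 88.0% and breach the limit; two give 92.0% and do not.

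| Assumed true survival | P(3 or more deaths in 25) | At least one of two arms |
|---|---|---|
| 91% | 0.394 | 63% |
| 93% | 0.253 | 44% |
| 95% | 0.127 | 24% |

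For 93%: 1 − (1 − 0.253)² = 0.44. Checked from the 10th patient per arm, the figure is about 61% (77% to 41%). Pooled over 50 patients, the limit is breached by 6 deaths (88.0%), with probability 14% at 93% and 4% at 95%.

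**The case against.** The case on the other side has several sound parts.

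- **The 80% is not an error.** A reader might infer that 50 patients cannot give it. The protocol's own base rate, sample size and one of its two named tests do give it.
- **At full enrolment the 30-point threshold is not loose.** It fires by chance in 2.6% of trials, and the smallest qualifying tables at 25 per arm (8 versus 0 up to 17 versus 9) have Fisher p between 0.004 and 0.046. The 24% and 30% figures need early or repeated looks, and the protocol schedules none.
- **The efficacy rule is discretionary.** Cessation is only considered, and the DSMC advises the Trial Steering Committee.
- **Section 10.6 might be read as contradicting 7.10.** It does not: looks on DSMC request are allowed, and section 9.4 has the DSMC reviewing safety data periodically. What remains is that neither section says when the limits are checked.
- **A halt might be read as losing the primary result.** It does not by itself: the feasibility proportion can be estimated from the hearts accrued, with less precision.
- **The DSMC charter** mentioned in 7.5 is not shown and may add detail.

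These points narrow the concern but do not remove it. The protocol sets no restriction on early looks at the efficacy gap. The safety halt is worded as mandatory, so a charter would have to qualify the protocol's own sentence. The per-arm reading is an inference from the reference to one of the treatments; if pooling is meant, the PGD limit is rarely crossed, but the text does not say so.

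**Conclusion.** The point holds in two parts.

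First, full-enrolment power for a true difference does not support acting on an observed 30-point gap before full enrolment. The risk is confined to early or repeated looks, and is moderated because cessation is only considered.

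Second, and more seriously, the halting limits apply a mandatory consequence to raw rates with no minimum number or allowance for sampling error. Read per arm, chance alone crosses the PGD limit in 14% of trials at 25 per arm, and in 42% with checks from the 10th patient. It crosses the survival limit in 24% to 63% at 25 per arm.

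The PGD figures rest on a true rate of 36% in both arms. The survival figures rest on an assumed 91% to 95%, and the 42% also on a frequency of checking that the protocol does not specify.

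**What to change.** In section 7.10:

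1. Delete the efficacy early-cessation sentence, or replace its power justification with a stringent significance boundary at a stated look. If the 80% is kept, leave the figure as it is and state its test (score), base rate (36% to 6%) and number (25 per arm).
2. Keep the DSMC's reference rates, but state that they apply per arm. Trigger DSMC review on an exact-binomial or posterior probability that the arm's true rate is worse than the reference, from a stated minimum number per arm and at named looks.
3. Record the resulting false-halt probability in the protocol or charter.
4. Cross-refer section 10.6 to these looks.

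The cost is protocol and charter wording. The downside is that a formal limit reacts slightly later than a raw rate; the DSMC can still act on individual events.
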